### **Background**

Endocuff Vision is a disposable device that fits over the end of a colonoscope. A row of flexible fingers extending from the device is used to flatten and deflect haustral folds during colonoscope withdrawal, which has been shown to improve adenoma detection, as well as detection of serrated polyps.

The Amplifeye device is a less expensive competitive device of similar design to the Endocuff Vision. Both Endocuff Vision and Amplify devices are FDA approved.

In this study, we propose to compare the Endocuff Vision and the Medivators AmplifEYE device in a randomized controlled trial using adenomas per colonoscopy as the primary endpoint. If the adenomas per colonoscopy with the Medivators device is shown to be non-inferior to Endocuff Vision, then the less expensive Medivators device could be used in place of the Endocuff Vision.

Both devices have been considered to be safe for use in clinical practice. Clinical trial evidence showing benefits of the Amplifeye device compared to no device have not been demonstrated.

### **Methods**

This will be a randomized controlled trial in patients age 40 and older undergoing colonoscopy for screening, surveillance, or diagnostic reasons. They will be randomized to one of two arms, i.e. High Definition colonoscopy with Endocuff Vision or High Definition colonoscopy with AmplifEYE.

A member of the research team will approach a potential subject to discuss participation in the study, including background of the proposed study, inclusion and exclusion criteria, benefits and risks of the procedures and follow-up. Prior to study enrollment, a subject must sign an informed consent document, which details the essential aspects of this study. The informed consent document will have prior approval of the study site's Institutional Review Board (IRB). Failure to obtain informed consent renders the subject ineligible for the study.

Data collected will include the type of scope used (adult versus pediatric); age; gender; indication; history of prior abdominal surgery and type; and identification of diverticulosis classified as mild, moderate, or severe. Additionally, exam time including insertion time, total procedure time, overall withdrawal time, and inspection time (withdrawal time minus anytime suctioning, cleaning, and diagnostic biopsy or therapeutic procedure) as well as retroflexion completion rates (ability to complete retroflexion) will be recorded. For each polyp, we will record the location, size, shape, and pathology. The bowel preparation will be evaluated and graded according to the Boston Bowel Preparation Scale. Complications including any mucosal trauma from the high definition colonoscope with Endocuff Vision or with AmplifEYE, perforation or gastrointestinal bleeding (requiring intervention) will be recorded.

## **Objectives**

The *primary endpoint* will be the number of conventional adenomas per colonoscopy of the Endocuff Vision Colonoscopy compared to that of the AmplifEYE colonoscopy. Adenomas per colonoscopy is calculated as the total number of adenomas detected divided by the total number of colonoscopies.

*Secondary endpoints* will include the following:

- Adenoma detection rate (calculated as the percentage of colonoscopies in which at least one adenoma was detected)
- Complications encountered during procedure (i.e., mucosal trauma, perforation, or gastrointestinal bleeding)
- Ability to pass device through the sigmoid colon (success rate of the device passing the sigmoid colon of the large intestine)
- Polyp detection rate
- Polyps per colonoscopy
- Exam times
  - *Total procedure time* – Total time of procedure from insertion to withdrawal
  - *Cecal insertion time* – Time of colonoscope insertion (from insertion into the rectum to the cecum)
  - *Overall withdrawal time* – Total time of colonoscope withdrawal (from cecum until the scope is withdrawn from the rectum)
  - *Inspection time* – Inspection time is defined the same as withdrawal time, but with the clock stopped for washing, suctioning, and polyp removal (or other non-inspection related activities)
- Cecal intubation rate (the success rate of reaching the cecum)
- Detection of serrated and flat lesions
- Retroflexion completion rate (ability to complete retroflexion)

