### **Statistical Analysis & Sample Size**

The primary endpoint will be the number of conventional adenomas per colonoscopy. Based on previous data (1) we estimate that the Endocuff Vision will result in an APC of 2.3. We consider that a clinically acceptable ADR for the Medivators device would be within 20% of this value or 1.84. To demonstrate non-inferiority, a sample size of 588 patients should be randomized.

With a sample size of 294 patients per group, the study will have 80% power to detect non-inferiority between the two groups, assuming tests using a one-sided two-sample t-test, a coefficient of variation 1.5 for both groups, and a noninferiority margin of 20%.

The number of conventional adenomas per colonoscopy will be compared between the Endocuff Vision and AmplifEYE groups using a two-sample t-test on the log-transformed adenoma count. Similar analyses will be performed for the number of polyps, serrated lesions, and flat lesions per colonoscopy. Two-sample t-tests (or Wilcoxon Rank Sum tests if non-normally distributed) will be used for comparisons of exam times. Chi-square tests will be used to compare the groups for differences in adenoma, polyp, serrated lesion, and flat lesion detection rates; complications; ability to pass the device through the sigmoid colon; and cecal intubation rate. A 5% significance level will be used for all tests.

In order to account for patient withdrawals, 20 additional patients will be enrolled in the study to ensure sufficient data will be included in the analysis.

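### A non-inferiority claim rests on one all-colonoscopies analysis, with no rule for exams finished without the assigned device, and these could push the false-claim rate above or below 5%

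*Combined protocol and SAP*

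**What the plan says.** The Background section sets out the inference sought: "If the adenomas per colonoscopy with the Medivators device is shown to be non-inferior to Endocuff Vision", the cheaper device could replace the other. It also places the device's action in the withdrawal phase: "A row of flexible fingers extending from the device is used to flatten and deflect haustral folds during colonoscope withdrawal". That sentence describes Endocuff Vision, and AmplifEYE is said to be of similar design.

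Objectives defines the primary endpoint over all exams: "Adenomas per colonoscopy is calculated as the total number of adenomas detected divided by the total number of colonoscopies". No exception is made for an exam in which the device failed. The same section lists as a secondary endpoint "Ability to pass device through the sigmoid colon (success rate of the device passing the sigmoid colon of the large intestine"), so failures are anticipated, and Statistical Analysis & Sample Size compares them by chi-square.

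That section gives one analysis of the primary endpoint, a two-sample t-test on the log-transformed count. It names no analysis population, no sensitivity analysis and no counting rule for failed device passage. Its only allowance is 20 extra patients for withdrawals, which are a different event. The data list under Methods includes scope type, exam times and complications, but no item for the device on the scope during withdrawal.

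**The concern.** An exam withdrawn without the assigned device tells us little about how well that device detects adenomas, yet under the stated formula its adenomas are credited to the assigned arm. In a superiority trial, mixing of this kind usually works against the claim. In a non-inferiority trial, mixing that brings the arms together works for it. AmplifEYE could then be declared an acceptable substitute partly on exams in which it was not used. The Background section adds to the stakes, because it says a benefit of AmplifEYE over no device has not been shown.

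**Working it through.** **Inputs from the documents.** Endocuff Vision mean: "we estimate that the Endocuff Vision will result in an APC of 2.3". Limit: "We consider that a clinically acceptable ADR for the Medivators device would be within 20% of this value or 1.84" (the sentence says ADR, but the value is an APC), so the ratio at the margin is 1.84/2.3 = 0.80. Power target: "the study will have 80% power to detect non-inferiority between the two groups". The sample-size model behind that target is stated as follows, with the last figure in per cent: "assuming tests using a one-sided two-sample t-test, a coefficient of variation 1.5 for both groups, and a noninferiority margin of 20". There are 294 patients per group and a 5% significance level.

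**Reproducing the plan's sample size.** On the log scale:

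- SD = √ln(1 + 1.5²) = √ln 3.25 = 1.0857
- Margin = −ln 0.80 = 0.2231
- SE at 294 per group = 1.0857 × √(2/294) = 0.0895

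With a true ratio of 1 and one-sided alpha 0.05, the noncentral t gives power 80.07% at 294, the smallest n that reaches 80%. The plan's figure reproduces, so this is the right model for the check.

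**Assumed inputs.** The documents give neither a failure rate f nor an APC c for exams finished without the assigned device. I take f = 2%, 5% and 10%, and c from 1.5 to 2.3. The log-scale SD is held at 1.0857, and the ratio of mixed means is treated as the shift on the log scale.

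**Formulas.** Set the true on-device ratio at the margin, with AmplifEYE 1.84 and Endocuff 2.3.

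- Both arms, common fallback: R = [1.84(1−f) + cf] / [2.3(1−f) + cf]
- Both arms swapped to the other device: R = [1.84(1−f) + 2.3f] / [2.3(1−f) + 1.84f]
- AmplifEYE failures only: R = [1.84(1−f) + cf] / 2.3
- Endocuff failures only: R = 1.84 / [2.3(1−f) + cf]
- False-claim rate ≈ Φ(−1.645 + ln(R/0.80)/0.0895). The noncentral t gives the same results to the precision shown, except for the last digit in a few cells; the table uses the t.

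**Worked case, f = 5%.** Common fallback with c = 2.3: R = (1.748 + 0.115)/(2.185 + 0.115) = 1.863/2.3 = 0.810, error 6.6%. Swap: R = 1.863/(2.185 + 0.092) = 1.863/2.277 = 0.818, error 8.2%. AmplifEYE only, c = 1.5: R = (1.748 + 0.075)/2.3 = 0.793, error 4.0%.

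| Scenario (nominal error 5%) | f = 2% | f = 5% | f = 10% |
|---|---|---|---|
| Both arms, common fallback, c = 1.5 | 5.4% | 6.0% | 7.2% |
| Both arms, common fallback, c = 2.3 | 5.6% | 6.6% | 8.5% |
| Both arms, swapped to the other device | 6.1% | 8.2% | 12.6% |
| AmplifEYE only, finished with Endocuff (c = 2.3) | 5.6% | 6.6% | 8.5% |
| AmplifEYE only, c = 1.84 | 5.0% | 5.0% | 5.0% |
| AmplifEYE only, c = 1.5 | 4.6% | 4.0% | 3.2% |
| Endocuff only, c = 1.5 | 5.9% | 7.4% | 10.6% |

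**The opposite risk.** If the devices are truly equal (both 2.3), only AmplifEYE fails and c = 1.5, power falls from 80% to 74% at f = 5% and 67% at f = 10%.

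**The case against.** Four objections deserve weight.

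- *Dividing by all colonoscopies is not an error.* It follows the randomised comparison, and failure to pass is part of whether one device can replace the other. This stands, and the analysis should be kept.
- *Removal or swapping is inferred.* A reader might infer that failed exams are finished without the assigned device and then counted. The documents say neither. Since cecal intubation rate is also an endpoint, an exam might simply be incomplete, and the same device on a different scope is not ruled out. This stands; what is established is the missing rule.
- *Failed exams can be identified.* A reader might infer from the Methods data list that they could not be separated later. The sigmoid endpoint requires success or failure to be recorded for each exam, and that list does not name every endpoint. The gap is narrower: no listed item shows which device, if any, was on the scope afterwards, or whether it came off later.
- *A per-protocol set selects on a post-randomisation event.* If AmplifEYE fails more often in difficult colons, excluding those exams could flatter it. This is correct, so that set cannot replace the all-randomised analysis and should be read beside the failure rates by arm.

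**Conclusion.** The concern holds as a gap in the plan for a non-inferiority claim. One all-exams analysis carries the claim, device failure is expected, and nothing says how exams finished without the assigned device are treated. A reader might go further and conclude that the formula favours a false claim. The documents do not support that, because the direction depends on which arm fails and on the fallback. At an assumed 5% of exams the error is about 6.0–6.6% with a common fallback in both arms, 8.2% with a swap in both arms, and about 4.0% if only AmplifEYE fails and the fallback APC is 1.5. At 2% the effect is small: 5.4–5.6% with a common fallback.

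These sizes rest on assumed failure rates and fallback APCs, and on the plan's log-scale model. Because neither size nor direction can be known beforehand, the rule should be fixed before the data are seen. This should be changed, but it does not invalidate the design.

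**What to change.** 1. In Methods, add one case report form item: device on the scope during withdrawal (assigned, none, other).
2. In Statistical Analysis & Sample Size, name the all-randomised analysis as primary and state that every randomised exam counts in its assigned arm.
3. Prespecify a per-protocol repeat of the primary analysis. It should exclude only exams withdrawn without the assigned device, not cecal intubations that failed for other reasons.
4. Claim non-inferiority only if the 20% margin is met in both sets. Selection in the per-protocol set then cannot produce a claim by itself.
5. Report failed-passage rates by arm beside the two results.

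How a failed passage is managed clinically is for the sponsor to specify.

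The cost is one field, one repeated analysis and slightly lower per-protocol power. From 294 per arm, assumed exclusions of 2%, 5% and 10% leave 288, 279 and 264, with power of about 79%, 78% and 76%. With the 20 extra patients (304 per arm) and no other losses, 297, 288 and 273 remain, with power of about 80%, 79% and 77%.

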## **Criteria**

All colonoscopies in the study will be done by [name]. Patients will be 40 and older and will be randomized to receive colonoscopy with the AmplifEYE device or with the Endocuff device.

### **Inclusion criteria**

- Undergoing colonoscopy for screening, surveillance, or diagnostic reasons
- Ability to provide informed consent
- 40 years and older

### **Exclusion criteria**

- Active inflammatory bowel disease
- Prior surgical resection of the colon
- Referred for resection of a polyp identified by another physician
- Referred for a previous incomplete colonoscopy
- History of polyposis syndrome or HNPCC

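### The known-polyp exclusion stops at polyps found by another physician, so return visits to the study endoscopist can add already-known adenomas to both arms and slightly favour non-inferiority

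*Combined protocol and SAP*

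**What the plan says.** Four parts of the combined protocol and SAP bear on this.

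- **Exclusion criteria.** Patients are excluded if "Referred for resection of a polyp identified by another physician". No other criterion deals with lesions already known. The exclusion for earlier surgical resection of the colon does not reach endoscopic resection.
- **Inclusion criteria.** The patient must be "Undergoing colonoscopy for screening, surveillance, or diagnostic reasons". Neither surveillance nor diagnostic is defined, and no therapeutic indication is listed.
- **Criteria.** "All colonoscopies in the study will be done by" is followed by one (redacted) name, so there is a single operator.
- **Objectives.** "Adenomas per colonoscopy is calculated as the total number of adenomas detected divided by the total number of colonoscopies". Lesions known before the procedure are not treated separately, and the polyp endpoints carry no such rule either.

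Statistical Analysis & Sample Size sets a relative margin. The control value is given as "we estimate that the Endocuff Vision will result in an APC of 2.3", and the test device must be "within 20% of this value or 1.84". The planned test compares log-transformed counts.

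**The concern.** The exclusion rests on a sound principle: finding a polyp whose position is already known says little about the device. As worded, it applies that principle only to polyps found by someone else. The study endoscopist also has patients of their own who return after an earlier examination. Two groups could be booked as surveillance or diagnostic: those coming for a site check or completion after an earlier endoscopic resection, and those being followed for a lesion left in place.

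Any adenoma tissue at such a site is likely to be found whichever device is fitted, because the operator knows where to look, and it then counts toward the primary endpoint. Adding the same amount to both arms moves their ratio toward 1. In a superiority trial that would be conservative. In a non-inferiority trial it raises the chance of accepting a device that is in fact at the margin. Adenoma and polyp detection rates and polyps per colonoscopy are open to the same dilution.

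**Working it through.** **Inputs from Statistical Analysis & Sample Size:** control mean 2.3; lowest acceptable mean 1.84, so the ratio is 1.84/2.3 = 0.80; "a coefficient of variation 1.5 for both groups"; 294 per group; one-sided test; 5% level; 80% power; analysis of log counts.

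**Assumed, because the documents give neither:** a share f of patients in each arm carries k known adenomas each, always found and always counted.

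**1. Reproduce the plan's sample size.**
- Log-scale SD = √ln(1 + 1.5²) = 1.0857.
- Margin = −ln 0.80 = 0.2231.
- n per group = 2 × 1.0857² × (1.645 + 0.842)² / 0.2231² ≈ 293 by the normal approximation. The noncentral t gives 294, with power 0.8007.
- The stated 294 therefore rests on this log-scale model at one-sided 5%. The same model is used below.

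**2. Add known adenomas on the log scale.** Take lognormal counts X with CV 1.5 and mean 2.3 (control) or 1.84 (test), so the true ratio sits at the margin. For each arm:
- mean log count = (1 − f)·E[ln X] + f·E[ln(X + k)], with the SD of the log count recalculated from the same mixture;
- observed ratio R = exp(test mean log − control mean log);
- SE = √[(SD₁² + SD₂²)/294], which is 1.0857 × √(2/294) = 0.0895 when f = 0;
- false non-inferiority rate = 1 − Φ(1.645 − ln(R/0.80)/SE).

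| Share f | Known adenomas k | Ratio R | SE | False non-inferiority rate |
|---|---|---|---|---|
| 0 | – | 0.800 | 0.0895 | 5.0% |
| 1% | 1 | 0.801 | 0.0894 | 5.1% |
| 5% | 1 | 0.804 | 0.0890 | 5.6% |
| 10% | 2 | 0.811 | 0.0903 | 6.8% |

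Example, last row: ln(0.811/0.80) = 0.0137; 0.0137/0.0903 = 0.151; 1 − Φ(1.645 − 0.151) ≈ 6.8%.

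**3. Check against a ceiling.** Known lesions affect only the patients who carry them. Even if those patients showed no device effect at all, R could not exceed 0.80^(1 − f), which is 0.818 at f = 10%. The 0.811 above respects that limit.

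The lognormal model has no zeros, whereas real adenoma counts do, so these rates are illustrative.

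**The case against.** **The inclusion criterion already keeps these patients out.** A reader might infer that anyone coming back to have a known polyp removed is eligible as long as the study endoscopist found it. The documents do not support that. Removal of a known polyp is a therapeutic reason, and only screening, surveillance and diagnostic reasons are listed, so on an ordinary reading such a visit fails inclusion whoever found the polyp. This part of the objection stands. It does not dispose of site checks, completion visits or follow-up of a lesion left in place, which can be labelled surveillance or diagnostic. The authors also thought a separate exclusion for known polyps necessary, and then confined it to other physicians' findings.

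**Lesions seen on imaging are covered.** Largely true. Another physician would normally report them, so a patient referred for resection meets the present exclusion.

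**The effect could be made to look large.** A reader who puts arithmetic means into the log-scale test would get (1.84 + 0.6)/(2.3 + 0.6) = 0.841 for 20% of patients with three known adenomas each, and a false non-inferiority rate of 14.0%. That ratio is above the ceiling of 0.80^0.8 = 0.837, so it cannot arise under the plan's log-count model. The calculation shown under the working gives 0.825 and about 9.4% for that case. Nothing in the documents suggests that such patients are this common. After a resection, residual conventional adenoma must also be present for there to be any effect.

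**Randomisation balances these patients.** True in expectation, so the issue is dilution and not imbalance between arms. On an absolute scale the expected difference of 2.3 − 1.84 = 0.46 would not change. But the plan states its margin as a percentage and tests log counts, so the ratio is the relevant scale.

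**The recorded data would allow a later check.** Partly true. Methods has indication and each polyp's location recorded, which would identify some cases. It does not record whether a lesion was known beforehand, so a clean sensitivity analysis is not assured.

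**Conclusion.** The gap in the wording is real but narrow. The exclusion omits lesions the study endoscopist already knows about, the counting rule has no provision for them, and undefined surveillance and diagnostic indications leave a way in. The resulting bias favours non-inferiority.

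Its size is probably small: a false non-inferiority rate of about 5.1% to 6.8% against a nominal 5%, over the range from 1% of patients with one known adenoma to 10% with two. These figures rest on assumed shares, on every known lesion being found with either device, on a true ratio exactly at 0.80, and on a lognormal approximation to counts. The documents show neither that such patients will be enrolled nor how many, so a reader should not infer that the primary conclusion is threatened. This is a minor point and a cheap improvement.

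**What to change.** Make two wording changes.

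1. **Exclusion criteria.** Replace the known-polyp exclusion with: *colonoscopy performed for resection, completion of resection, or site check of a lesion already identified by any physician, including the study endoscopist.*
2. **Objectives.** Add to the endpoint definition: *lesions whose location was known before the procedure, including residual tissue at a previous resection site, are not counted as detected adenomas or polyps.*

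The second change needs a tick-box per polyp on the case report form, marking whether the lesion was known before the procedure. A few otherwise eligible patients of this endoscopist would be screened out, which may slow recruitment slightly. The sample size stays at 294 per group.

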## **Randomization**

Once a patient has been screened to ensure the inclusion and exclusion criteria have been met and has provided consent for participation in the study, the subject will be randomized in a 1:1 ratio. Randomization outcomes include the Endocuff Vision Colonoscopy or the AmplifEYE Colonoscopy.

### **Statistical Analysis & Sample Size**

The primary endpoint will be the number of conventional adenomas per colonoscopy. Based on previous data (1) we estimate that the Endocuff Vision will result in an APC of 2.3. We consider that a clinically acceptable ADR for the Medivators device would be within 20% of this value or 1.84. To demonstrate non-inferiority, a sample size of 588 patients should be randomized.

With a sample size of 294 patients per group, the study will have 80% power to detect non-inferiority between the two groups, assuming tests using a one-sided two-sample t-test, a coefficient of variation 1.5 for both groups, and a noninferiority margin of 20%.

The number of conventional adenomas per colonoscopy will be compared between the Endocuff Vision and AmplifEYE groups using a two-sample t-test on the log-transformed adenoma count. Similar analyses will be performed for the number of polyps, serrated lesions, and flat lesions per colonoscopy. Two-sample t-tests (or Wilcoxon Rank Sum tests if non-normally distributed) will be used for comparisons of exam times. Chi-square tests will be used to compare the groups for differences in adenoma, polyp, serrated lesion, and flat lesion detection rates; complications; ability to pass the device through the sigmoid colon; and cecal intubation rate. A 5% significance level will be used for all tests.

In order to account for patient withdrawals, 20 additional patients will be enrolled in the study to ensure sufficient data will be included in the analysis.

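### The stated 80% power rests on an unstated log-normal model that counts with zeros cannot follow; for the 20% margin set on APC, the plan's own CV of 1.5 gives about 49–56%

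*Combined protocol and SAP*

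**What the plan says.** The Objectives section defines the primary endpoint as an arithmetic mean: "Adenomas per colonoscopy is calculated as the total number of adenomas detected divided by the total number of colonoscopies". The same section lists the adenoma detection rate, the share of examinations with at least one adenoma, so the plan itself expects patients with a count of zero.

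The Statistical Analysis & Sample Size section then sets out:

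- **Control value:** "Based on previous data (1) we estimate that the Endocuff Vision will result in an APC of 2.3".
- **Margin:** an acceptable result for the other device "would be within 20% of this value or 1.84". The sentence calls this an ADR, but 1.84 is 80% of the APC of 2.3.
- **Power:** "With a sample size of 294 patients per group, the study will have 80% power to detect non-inferiority between the two groups", assuming a one-sided two-sample t-test, "a coefficient of variation 1.5 for both groups, and a noninferiority margin of 20" percent.
- **Primary analysis:** a comparison "using a two-sample t-test on the log-transformed adenoma count".
- **Level:** 5% for every test.

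No distribution is named. Nothing says how a zero count is to be logged, or how the 20% margin is carried to the log scale.

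**The concern.** The endpoint and the margin are on the arithmetic mean, while the analysis is on the log scale. The power sentence names no scale, although its figure turns out to be a log-scale one. The scales agree only under a model such as the log-normal with equal CVs, and a variable that takes the value zero cannot be log-normal.

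The error can run in either direction, depending on the missing zero rule. A test of the APC margin itself has well under 80% power. A log-count test against ln(0.80) can look adequately powered and yet often pass AmplifEYE when it loses the full 20% of adenomas. The second error bears on the purpose of the trial: the Background section says that if non-inferiority is shown, "then the less expensive Medivators device could be used in place of the Endocuff Vision".

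**Working it through.** **Inputs.** From Statistical Analysis & Sample Size: n = 294 per group, control APC 2.3, limit 1.84 (difference 0.46, ratio 0.80), CV 1.5, 5% level used one-sided. Assumption, not stated in the plan: the devices are truly equal.

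**1. Reproducing the 80%.** Log-normal SD = sqrt(ln(1 + 1.5²)) = sqrt(ln 3.25) = 1.0857. Margin = ln(1/0.80) = 0.2231. SE = 1.0857 × sqrt(2/294) = 0.0895, and 0.2231/0.0895 = 2.49. The noncentral t gives power 80.07% at n = 294 and 79.96% at n = 293, so 294 is the smallest n that reaches 80%. Variants that do not reproduce it: one-sided 2.5% (70%), a margin of ln(1.2) (65%), and the two APC tests below.

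**2. The margin as a difference in APC.** SD = 1.5 × 2.3 = 3.45. SE = 3.45 × sqrt(2/294) = 0.2845, and 0.46/0.2845 = 1.617. Power = Φ(1.617 − 1.645) = 49%. About 697 per group would be needed for 80%.

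**3. The margin as a ratio of APCs.** SE of the log ratio of means = 1.5 × sqrt(2/294) = 0.1237, and 0.2231/0.1237 = 1.804. Power = Φ(1.804 − 1.645) = 56%. For 80%, n = 2 × 2.25 × (2.4865/0.2231)² = 559 per group. With 294 per group, 80% power corresponds to a ratio of exp(−2.4865 × 0.1237) = 0.735, or to a CV of 0.2231/(2.4865 × sqrt(2/294)) = 1.09 in place of 1.5. If all 20 extra patients were also analysed (304 per group), power would be only 50% (difference) or 57.5% (ratio).

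**4. Does the planned log-count test rescue the 80%?** This step needs a count distribution, which the plan does not give. Assume a negative binomial with mean 2.3 and CV 1.5: k = 2.3²/(3.45² − 2.3) = 0.551, and P(0) = (k/(k + 2.3))^k = 0.404. At APC 1.84, keep either k or the CV the same; ranges cover both. The power and false non-inferiority columns come from 40,000 simulated trials. The first four rows test against ln(0.80).

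| Analysis | Power, equal devices | False non-inferiority at APC 1.84 (5% intended) | APC 1.84 as a ratio on the log(count + c) scale | Power if the log margin is set at that ratio |
|---|---|---|---|---|
| log(count + 0.1) | 46% | 7–10% | 0.82–0.84 | 32–40% |
| log(count + 0.5) | 81% | 27–33% | 0.875–0.887 | 38–44% |
| log(count + 1) | 95% | 56–61% | 0.90–0.91 | 41–46% |
| zeros dropped | 80% | 29–33% | – | – |
| ratio of means, empirical SE | 57% | 5% | – | – |
| difference of means | 50% | 5% | – | – |

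The two rules that seem to confirm 80% (adding 0.5, dropping zeros) pass a device at the margin five to seven times as often as intended. The two tests on APC itself hold about 5% and agree with steps 2 and 3.

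**The case against.** The strongest reply is that the plan is consistent on its own terms. It specifies a log-scale t-test, and 80% is correct for a log-scale t-test. Under log-normality with a CV of 1.5 in both groups, the ratio of geometric means equals the ratio of APCs, so ln(0.80) is the 20% APC margin. On this view the 49–56% describes tests that the plan does not contain.

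Much of this is right. The 80% is not an arithmetic slip, the log scale is named in the next paragraph, and 49–56% is conditional on testing the margin where the plan sets it. The argument fails at the zeros: the plan's own detection-rate endpoint presupposes them, and their logarithm does not exist.

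A second point is that the false non-inferiority figures depend on an assumed distribution and constant. That stands as a limit on their precision. With a Poisson–log-normal of the same mean and CV (about 30% zeros), the rates are 4.5%, 22% and 54% for constants 0.1, 0.5 and 1, so not every zero rule inflates the error. The range itself shows that the unstated rule decides the result.

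A third point is that a smaller correction might do: state the zero rule and the log-scale margin and keep the test. If that margin is matched to APC 1.84, power under the assumed negative binomial is only 32–46%, so this does not recover 80% either.

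**Conclusion.** The concern holds. The 80% belongs to a log-normal calculation that adenoma counts cannot satisfy. For the margin that the plan sets on APC, its own n and CV give 49% power (difference) or 56% (ratio), assuming equal devices and one-sided 5%. Those two figures, and the fact that log(0) is undefined, need no assumed count distribution.

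The false non-inferiority rates do need one and are illustrative: 7–61% under the negative binomial across the zero rules examined. They show that common ways of running the planned test against ln(0.80) fail to control error at APC 1.84. This should be corrected before analysis, because the primary test cannot be run as written and the zero rule could otherwise be chosen with the data in view.

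**What to change.** In Statistical Analysis & Sample Size, replace the primary t-test on log counts with:

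> The primary analysis estimates the ratio of mean adenomas per colonoscopy (AmplifEYE / Endocuff Vision) from a log-link count model with robust standard errors, zeros included. Non-inferiority is concluded if the one-sided 95% lower confidence limit exceeds 0.80.

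Then replace the 80% statement with:

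> With 294 per group, CV 1.5 and equal true APC, power to exclude an APC ratio of 0.80 at one-sided 5% is about 56%; 80% power corresponds to a ratio of about 0.735.

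The cost is two text changes and no extra patients, but the stated power becomes less favourable: about a 44% chance of failing to show non-inferiority between truly equal devices. If the sponsor wants 80% at the ratio margin with a CV of 1.5, the trial needs about 559 per group (2 × 559 = 1,118, against 588). If earlier data support a CV near 1.09 for the raw counts, 294 per group would suffice, and the plan should give that evidence.
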